4. If applicable, upload a Co	ost Analysis form here:
: HM20007902	View: SF - Standard of Care Vs. Research Costs

Standard of Care Vs. Research Costs

1. *Describe any procedures, therapy, lab work, x-rays, drugs, or devices, etc that are considered standard of care and will be charged to the participant or their insurance:

All associated procedures involving anesthesia, abiation, hospitalization, post procedure holter monitors and post procedure office visits are considered standard of care and will be charged to participant and their insurance.

2. Describe the process to determine whether participants' insurance will cover the expenses: Patients will have the procedure and all associated expenses submitted to insurance as standard of care.

ID: HM20007902

View: SF - Compensation

Compensation

- Describe any compensation that will be provided including:
 Items such as parking/transportation

 - total monetary amount
 - type (e.g., gift card, cash, check, merchandise, drawing, extra class credit)
 how it will be disbursed:

No compensation.

2. If compensation will be pro-rated, explain the payment schedule:

ID: HM20007902

View: SF - Risks, Discomforts, Potential Harms and Benefits

Risks, Discomforts, Potential Harms and Benefits

- Describe the risks to participants associated with this study:

 physical, psychological, social, legal, financial, and other risks
 - seriousness of given risks
 - probability or likelihood of given risks

The risks of LMA airway management in atrial fibrillation abiation are: gastric aspiration, intraoral trauma, intraoral nerve paisies, largynospasm, incorrect placement, need for conversion to ETT, sore throat, pulmonary edema, bronchoconstriction

The risks of ETT airway management in atrial fibriliation abiation are: oral injury, dental injury, incorrect placement, hoarseness, sore throat, laryngospasm, laryngeal injury, difficulty swallowing.

There is a potential risk of loss of condifentiality.

2. Describe how the risks / harms will be minimized:

Risks/harms will be minimized as patient data will be carefully managed and accessible by minimum necessary study personnel. Risks are minimized as both groups will have anesthetic plans that have been proven safe and standard of care in a wide variety of clinical

- If the disclosure of any of the information obtained during the study would place the individual at risk for harm (legal, reputation, emotional etc.) and the information will be recorded so that the individual could be identified, explain the protections that will be put in place to decrease the risk of disclosure:
- 4. * The Code of Virginia requires that most medical personnel and all employees of institutions of higher education report suspected child/elder abuse or neglect. Is it likely investigators could discover information that would require mandatory reporting by the investigators or staff:
 - Yes
 - No
- 5. Is it likely investigators could discover a participant's previously unknown condition (eg disease, suicidal thoughts, wrong paternity) or if a participant is engaging in illegal activities:
 - Yes
 - No
- 6. If yes, explain how and when such a discovery will be handled:
- 7. Describe any potential risks or harms to a community or a specific population based on study findings: There is minimal to no risk or harms to a community or specific population based on study findings.
- Pescribe criteria for withdrawing an individual participant from the study; such as safety or toxicity concerns, emotional distress, inability to comply with the protocol, etc.:

Participants will be withdrawn from the study if they are converted from their initial randomization. They will also be withdrawn if they request to be removed from study. Patients who do not complete all the post discharge holter monitor evaluations will be kept in the study, and the missed data fields will not be evaluated for that specific patients

- Summarize any pre-specified criteria for stopping or changing the study protocol due to safety concerns:
 No specified criteria for stopping or changing study protocol for safety concerns.
- 10. Where appropriate, discuss provisions for ensuring necessary medical, professional, or psychological intervention in the event of adverse events to the subjects:
- 11. Describe any potential for direct benefits to participants in this study: Participants in this study have potential for benefits of possibly fewer side effects, while also having a similar outcome with regards to

12. * Describe the scientific benefit or importance of the knowledge to be gained: The scientific benefit of knowing if the use of LMA is associated with similar (non-inferior) outcome in term of procedure length and

determining if the side effects and patient satisfaction are superior could improve the anesthetic care of patients undergoing abiation of

- 13. If applicable, describe alternatives (research or non-research) that are available to potential participants if they choose not to participate in this study:
- 14. Indicate if this study will have a Data Safety Monitoring Board (DSMB) or a Data Safety Monitoring Plan (DSMP): [Required for all Full Review studies)

DSMB Review Required
✓ DSMP Required
Not Required

ID: HM20007902

View: SF - DSMP Details

DSMP Details

1. Describe your Data Safety Monitoring Plan for monitoring the data collected to ensure the safety of participants. Data collection will be done in a timely manner, with initial data input within a week of each visit. After the first 25 patients are enrolled an Interim analysis of primary outcomes as well as adverse outcomes will be done to determine if there is an association between either group and increased incidence of adverse outcomes. If an association is seen the IRB will be notified and the project design reevaluated.

View: SF - Consent Qualifiers ID: HM20007902

Consent Qualifiers

- 1. Are you submitting your study as exempt and therefore no consent is required:

No

ID: HM20007902

View: SF - Consent Groups

Consent Groups

1. " List all consent groups:

Group	Types	Waivers	Roles	Roles Consent	Coercion	Decision	Status Change
				Other			Onlang
Qualified Patients	Consent by	Walvers	Principal Investigator	Consent will be obtained in the	approached by study personnel and given facts of r study, no coercion will be utilized to encourage	e Patients will be y given from time approached by study personnel unti medications which may after decision making ability are given. Approximately 30 minutes to 1 hour	
	Participant	Requested	Co/Sub- Investigator	preoperative holding s area prior to procedure. Consent			ı
			Research Coordinator	will be obtained prior to patient receiving			
			Research Assistant	any medications which would potentially interfere			
			Trainee/Student			prior to procedure start.	
Patient Screening	None of the Above (select	Walver of Some or	Principal Investigator	No consent will be obtained	No consent will be obtained	No consent will be obatined	
	walver below)	All Elements of Consent	Co/Sub- Investigator				
		or consent	Research Coordinator				
			Trainee/Student				

2. Upload any consent / assent documents:

ID: HM20007902

View: SF - Waiver of Some or All Elements of Consent

Waiver of Some or All Elements of Consent

Consent groups that require a waiver of some or all elements of consent:

Group	Roles - Other	Consent	Coercion	Decision	Status Change	
Patient Screening		No consent will be obtained	No consent will be obtained	No consent will be obatined		

The basic elements of informed consent are as follows:

- 1. All of the following:
 - a statement that the study involves research
 - an explanation of the purposes of the research
 - an explanation of the expected duration of the participant's involvement
 a description of the procedures to be followed

 - Identification of any procedures which are experimental

- 2. A description of any reasonably foreseeable risks or discomforts to the participant
 3. A description of any benefits to the participant or to others which may reasonably be expected from the research
 4. A disciosure of appropriate alternative procedures or courses of treatment, if any, that might be advantageous to the participant
 5. A statement describing the extent, if any, to which confidentiality of records identifying the participant will be maintained
 6. For research involving more than minimal risk, an explanation as to whether any compensation and an explanation as to whether
- any medical treatments are available if injury occurs and, if so, what they consist of, or where further information may be obtained 7. An explanation of whom to contact for answers to pertinent questions about the research and research participants' rights, and
- whom to contact in the event of a research-related injury to the participant A statement that participation is voluntary, refusal to participate will involve no penalty or loss of benefits to which the participant is
 otherwise entitled, and the participant may discontinue participation at any time without penalty or loss of benefits to which the participant is otherwise entitled
- 1. Describe which of the elements of informed consent you are waiving or altering for each group listed at the top of this page: All elements of consent will be waived for this group. This group will consist of the individuals listed on the electrophysiology procedure schedule whose charts will be reviewed for possible eligibility for study recruitment. These patients charts will be accessed by the minimum necessary study personnel. The walver is requested so appropriate screening can be done without undue burden on patients or study personnel.

2. Will you be waiving parental permission for any of the consent groups at the top of this page: O Yes No
3. Is this study sanctioned by State and Local Government and designed to study public benefit or service programs: Yes No
D: HM20007902 View: SF - Walver [45 CFR 46.116d] - Adults
Waiver [45 CFR 46.116d] - Adults
1. Explain how the research involves no more than minimal risk to the participants: This portion of the research involved no more than minimal risk as this portion will involve screening of potential patients for possible recruitment. The minimum necessary study personnel will evaluate patients chart for eligibility. No change in patient care will occur.
2. Explain how the waiver or alteration will not adversely affect the rights or welfare of the participants: Participants rights or welfare will not be affected as there will be no change in patient care secondary to the screening, and the screening will be done by only study personnel and the minimum necessary chart evaluation will be done.
3. Explain how the research could not practicably be carried out without the walver or alteration: Walver is requested so that patients can be properly screened for possible inclusion into research study. Without screening patients the study personnel would not be able to properly evaluated and enroll potential participants.
4. Explain how participants will be provided with additional pertinent information after participation. If this will not be provided, explain why not: Patients will not be provided additional pertinent information, as this will be a simple chart review for eligibility for the study.
D: HM20007902 View: SF - Documents
D: HM20007902 View: SF - Protocol Complete
•
€

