At VCU Health system, Anesthesiologists have been successfully using LMA (General Anesthesia) for ablation in PAF in eligible patients for over five years. The investigators are proposing a randomized, single blind study to evaluate the use of LMA versus ETT in this patient population. A concurrent retrospective study will be conducted to evaluate the last two years data of outcomes in this patient population at VCU. The investigators wish to do a prospective study to reduce bias, as the patients who have greater comorbidities are more likely to have ETT for an esthesia, and we believe this will skew the retrospective data when it is collected. The LMA used at VCU Health are LMA Supreme (Teleflex Medicals, Ireland). The study is designed as a non-inferiority study with a primary outcome of procedure length.

Secondary outcomes will include flouroscopy duration, total anesthesia time, total intra- and post- procedure opioids and ionotropes/pressors/chronotropes, patient satisfaction, PAF recurrence.

Briefly describe the study design, including all interventions or interactions with research participants and access to identifiable data. Use lay language whenever possible.

This will be a prospective, randomized single blind study comparing the use of general anesthesia with endotracheal tube versus laryngeal mask airway in patients undergoing abiation for paroxysmal atrial fibrillation. Patients will be consented the morning of the procedure and will be conducted only by study personnel. All patient identifiers will be stored in a separate, password protected document from data set. Patients will be randomized, data collected and stored in the secure REDCAP database. REDCap database randomization software will be used to randomize patients into one of the two study groups. Patients will be randomized after they sign informed consent the morning of the procedure. Randomization will be done by study personnel using REDCap and verbally conveyed to anesthesia provider that morning of procedure. The minimum necessary study personnel will have access to patient identifiers.

Power analysis: Estimated mean procedure time 3 hours, range 1.5-4.5 hours, standard deviation 0.9, n = 82 to detect 0.5 hour margin of non-inferiority between the two groups. Including 5% drop-outs, final n=87. Goal enrollment 44 patients per group.

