See 949	Use of Internet for Data Collection Registries/Repositories (Includes Accessing, Contributing or Creating) None of the Above Rect all Identifiers that will be collected as part of this study (Including for recruitment, data gathering, data analysis, etc. in if the data will eventually be anonymized: Names Geographic Locators Below State Level Social Security Numbers Dates (year alone is not an identifier) Ages >89 Phone Numbers F-acsimile Numbers E-mail Addresses Medical Record Numbers Blometric Identifiers Web URLs IP Addresses Account Numbers Health Plan Numbers Full Face Photos or Comparable Images License/Certification Numbers Vehicle ID Numbers

- 4. "Will participants be able to withdraw their data (paper, electronic, or specimens) from the study if they no longer wish to participate:

	Ye No.	
5.	Patient hospita	above, describe how participants will be able to withdraw their data: ts will be given a copy of consent form with contact information of study PI's and will be able to withdraw after discharge from the al by contacting those individuals. During hospital stay the care teams will have contact information for study personnel in case a wishes to withdraw during their hospitalization.
ID: HN	M20007	902 View: SF - HIPAA
HIP	PAA	
1.		ribe the protected health information that will be obtained or used in this research: ollection:
	Demog	graphics: age, race, comorbidities (diabetes, hypertension, coronary artery disease), weight, and height
	Proced	fure time: Will be measured as time from start of procedure to end of procedure, as recorded in minutes
	Fluoro	scopy time: As measured and reported by electrophysiology and radiology notes, recorded in minutes
		nesthesia time: Total anesthesia time as measured in minutes and recorded in the anesthesia record, from anesthesia start time to esia stop time
	Time to	o discharge from PACU: time from arrival to PACU until discharge from anesthesia care
		ntra-procedure opioids: Measured in total amount of opioids required during procedure, if different opioids used will convert to oral ine equivalents
	Anesth	etic Requirements: average end tidal volatile anesthetics, average amount of intravenous anesthetics
		perative hemodynamics: average heart rate, maximum heart rate, minimum heart rate, average MAP, minimum systolic blood re, maximum systolic heart rate, minimum diastolic blood pressure, maximum diastolic blood pressure

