		ocedure pressor/lonotrope/chronotrope requirements: total measured amounts of all pressors/lonotropes and chronotropes stered intraoperatively
	Electro proced	ophysiology Parameters: size of left abrium (mm), left ventricular ejection fraction; duration of paroxysmal abrial fibrillation prior to ure
		trauma: Any noted trauma in the anesthesia or post-procedure notes, including damage to lips/leeth, laryngospasm, need for ation post procedure
	Post-p	rocedure nausea: Measured by number of doses of antiemetics given in the post-procedure time period.
	Post-p	rocedure emesis: Measured by number of times patient has emesis during post-procedure time period.
	proced	ibriliation recurrence: defined as recurrence of paroxysmal atrial fibriliation recurring at any time after 6 weeks past the day of lure. As standard of care these patients are followed up with Holter monitoring for a period of 6 months. Holter monitoring will be or 48 hour time periods immediately post-procedure, 2 weeks, 6 weeks, 4 months and 6 months post procedure as is standard of
	Aspira	tion events: aspiration events as noted in the anesthesia, PACU and post procedure notes would be documented.
		t Satisfaction: patients will be given an survey by study personnel prior to discharge from the hospital; survey will be conducted in by study personnel
	Cost A	nalysis: an analysis of cost to patient as well as overall hospital costs will be conducted
2	Informa	ribe the source(s) of the protected health information: ation will be collected both by reviewing data from the medical record of VCU Health, Cemer as well as by in person surveys cled prior to hospital discharge.
3.	PHI co	ain how the PHI collected or used in this research is the minimum necessary to accomplish this research: illected is minimum necessary to determine our primary and secondary outcomes in determining if the use of LMA is non-inferior to r abilation for atrial fibriliation.
4	. * Selec	ct all pathways this research will employ to use or access PHI:
		- Marine a Robert
		e-Identified Data
	u	mited Data Set
	_ W	laiver of Authorization
	₽ P	artial Walver of Authorization
	₹ \$	igned Authorization Combined with Consent Form
	S	gned Authorization as Stand-Alone Form

De-Identified Data	
Limited Data Set	
Waiver of Authorization	
✓ Partial Waiver of Authorization	
Signed Authorization as Stand-Alone Form	

View: SF - Partial Walver of Authorization

Partial Waiver of Authorization

ID: HM20007902

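### Operator and ablation technique are not among the listed data or named as covariates for the primary outcome of procedure length: a cheap precision gain of unknown size may be forgone

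*Combined protocol and SAP*

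**What the plan says.** - **Outcome.** SF - Research Description: "The study is designed as a non-inferiority study with a primary outcome of procedure length". SF - HIPAA, item 1, defines procedure time: "Will be measured as time from start of procedure to end of procedure, as recorded in minutes".
- **Allocation.** SF - Research Description, item 4: "REDCap database randomization software will be used to randomize patients into one of the two study groups". No strata, blocks or minimisation factors are mentioned.
- **Sample size.** The same item, repeated in SF - Study Population, item 3: "Estimated mean procedure time 3 hours, range 1.5-4.5 hours, standard deviation 0.9", with "n = 82 to detect 0.5 hour margin of non-inferiority between the two groups". Then "Including 5% drop-outs, final n=87" and "Goal enrollment 44 patients per group". Alpha, sidedness and power are not stated.
- **Data to be collected.** SF - HIPAA, item 1, lists demographics, comorbidities, times, drugs, haemodynamics and the electrophysiology parameters: "size of left abrium (mm), left ventricular ejection fraction; duration of paroxysmal abrial fibrillation prior to" the procedure. SF - Existing Data/Specimen Details adds diagnoses, laboratory data and body size. Neither list includes the ablation operator, the technique or the energy source.
- **Analysis.** No model for the primary outcome is given, so no covariate is specified.
- **Setting.** VCU is the only site ticked. Eligibility requires a primary ablation for paroxysmal atrial fibrillation and does not fix the technique. The number of operators and techniques in use is not stated.

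**The concern.** The outcome is the duration of a procedure, so the person doing it and the method used are natural candidates for explaining its variation. The listed electrophysiology variables describe the patient only. If operator and technique do matter, their contribution stays in the error term of an unadjusted comparison. The confidence interval for the difference between arms is then wider than it needs to be.

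Precision is not in surplus here. The stated sample size gives about 80% power, and only at a one-sided 5% level; at one-sided 2.5% it gives about 70%. A covariate that explains part of the variance would raise power without a single extra patient.

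**Working it through.** **Inputs from the documents:** margin 0.5 h, SD 0.9 h (variance 0.81), 82 evaluable (41 per arm), 5% drop-out, 44 per arm enrolled. **Inferred:** true difference 0, one-sided alpha 0.05, power 80%. **Assumed:** share of variance explained by operator and planned technique, R² = 0 to 0.40.

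**1. Reproduce the plan's figure.** n per arm = 2 × SD² × (z₁₋α + z₁₋β)² / margin² = 2 × 0.81 × (1.645 + 0.842)² / 0.25 = 40.1, rounded up to 41, so 82 in total. A noncentral-t calculation also gives 82. Drop-out: 82 / 0.95 = 86.3, rounded up to 87. One-sided 2.5% with 80% power would need 102 (104 by the t calculation), so the plan's figure matches one-sided 5%, with no allowance for covariates.

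**2. Power with adjustment.** Residual SD = 0.9 × √(1 − R²). Power is from the noncentral t with 41 per arm, charging 4 degrees of freedom for covariates (76 left of 80).

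| Assumed R² | Residual SD (h) | Power, one-sided 5% | Power, one-sided 2.5% | Total N for 80% power, one-sided 5% |
|---|---|---|---|---|
| 0 | 0.900 | 80.2% | 70.0% | 82 |
| 0.10 | 0.854 | 83.7% | 74.5% | 74 |
| 0.20 | 0.805 | 87.3% | 79.3% | 66 |
| 0.30 | 0.753 | 90.9% | 84.3% | 58 |
| 0.40 | 0.697 | 94.2% | 89.4% | 50 |

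In the R² = 0 row, spending the 4 degrees of freedom changes power by less than 0.1 point.

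**3. What R² might mean in practice.** Two operators who share cases equally and differ by D hours contribute variance D²/4.
- D = 0.5 h: 0.0625 / 0.81 = 7.7%; power at one-sided 5% is 82.9%.
- D = 1.0 h: 0.25 / 0.81 = 31%; power is about 91%.
- To reach 40% from operator alone, D = 2 × √(0.40 × 0.81) = 1.14 h. The top of the assumed range therefore needs a larger gap or a contribution from technique.
- One operator and one technique: R² = 0 and no gain.

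**4. Chance imbalance between arms.** With 44 per arm and equal shares, the SD of the difference in operator proportions is √(2 × 0.25 / 44) = 0.107. The 95% range of the resulting shift is 1.96 × 0.107 × D = 0.10 h (D = 0.5) to 0.21 h (D = 1.0), which is 21–42% of the margin. The full 95% half-width for the difference is about 1.96 × 0.9 × √(2/44) = 0.38 h. At D = 1.0 the ratio (0.21 / 0.38)² = 0.31 is the same 31% as in step 3. The shift is the operator share of the existing sampling error, counted once already in the SD of 0.9.

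**The case against.** The plan can fairly be defended on several grounds, and most of them limit the point.

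- **A reader might infer that allocation is simple randomisation.** The text does not say so. It is a brief lay description and is silent on blocks and strata. Likewise, the absence of adjustment is not a chosen unadjusted analysis: no primary model is given at all, which is a wider gap.
- **A reader might infer that the variance can never be removed later.** The documents point the other way. Data come from the medical record, fluoroscopy time is taken from electrophysiology and radiology notes, and the linking key is kept until collection and analysis are complete. Operator and technique could probably be retrieved. What retrieval cannot restore is prespecification.
- **A reader might infer that operator imbalance threatens the result beyond sampling error, or biases it.** It does neither. Randomisation keeps the unadjusted comparison valid, and step 4 shows that the shift is already inside the confidence interval.
- **The data list answers a question about protected health information.** Operator identity is not patient health information, so its absence there is weaker evidence than absence from a case report form, and the REDCap form is not in the documents. This is a fair caution, but no other section names either variable.
- **The size is unknown and may be zero.** This stands. The variance share is an assumption, and the range must start at 0.
- **Adjusting for technique could itself introduce bias** if technique is chosen or changed after allocation. Patients are randomised on the morning of the procedure, and nothing says when technique is fixed. This also stands, and it limits the covariate to the technique planned beforehand.

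**Conclusion.** The point holds as a cheap efficiency gain of unknown size, not as a flaw in validity. As written, the plan lists neither operator nor technique and prespecifies no use of them in the primary comparison. Under an assumed variance share of 0–40%, adjustment would change power by 0 to 14 points at one-sided 5% (80% to 80–94%) and by 0 to 19 points at one-sided 2.5% (70% to 70–89%), with 41 per arm, SD 0.9 h, margin 0.5 h and no true difference. If the only source is two equally busy operators 0.5 h apart, the gain at one-sided 5% is under 3 points. Confidence in the size is low because it depends on how many operators and techniques the site uses, which the documents do not say. The recommendation rests on the very small cost rather than on a demonstrated loss.

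**What to change.** 1. Add two fields to the REDCap data list: the ablation operator, and the ablation technique (energy source) planned before randomisation. Both are likely to be available from the electrophysiology schedule or notes. Technique should be entered as planned, not as finally performed.
2. When the primary analysis is written, prespecify both as covariates in the non-inferiority comparison of procedure time. For example, use a linear model with arm, operator and planned technique, and compare the confidence limit for the arm difference with the 0.5 h margin.
3. If there are only a few regular operators, optionally build the REDCap allocation table in permuted blocks within operator. Otherwise adjust only, since 44 per arm does not support many strata.
4. State how many operators and techniques are in use. If there is one of each, steps 1 to 3 can be dropped.

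The cost is two chart fields, a sentence in the analysis plan, a few degrees of freedom (under 0.1 point of power if the factors explain nothing) and, if blocking is chosen, a change to the allocation table. Patient care and sample size are unaffected.

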View: SF - Research Description

Research Description

1. Describe the study hypothesis and/or research questions. Use lay language whenever possible.

The hypothesis of this prospective single bilind randomized trial is that general anesthesia with laryngeal mark airway is non-inferior in length of procedure to endotracheal tube for patients undergoing abiation for atrial fibrillation.

Secondary hypothesis:
The secondary hypothesis is that general anesthesia with LMA is superior or non-inferior to endotracheal tube in duration of fluoroscopy, post procedure side effects, patient satisfaction and recurrence of PAF.

Describe the study's specific aims or goals. Use lay language whenever possible.
 Study goal is to determine if the use of laryngeal mask airways in abiation of atrial fibrillation is non-inferior to endotracheal tube in terms of procedure length.

3. Describe the study's background and significance, including citations, or upload a citation list in document upload. Use lay

language whenever possible.

In recent years it has been shown that catheter abiation of symptomatic atrial fibrillation (PAF) is superior to antiarmythmic drug therapy with regards to effectiveness and clinical outcomes. 1 Atrial fibrillation is the most common cardiac arrhythmia, with high rates of concomitant heart failure, stroke and mortality.2,3 During an abiation procedure, a patient can be managed with intravenous sedation or General Anesthesia. Within this setting, General anesthesia is associated with improved procedure time and cure rate compared to

Airway management during GA can be achieved through a LMA or an ETT. The use of LMA compared to ETT has been shown in different surgical populations to decrease procedure and recovery time, improve hemodynamic stability and reduce anesthetic requirements.5,6,7 it has also shown to decrease airway complications, and postoperative nausea/vomiting which are important factors that affect overall patient satisfaction.8,9,10,11,12

Although general anesthesia in electrophysiology procedures is associated with a higher cure rate, there have been reports of increased airway trauma.13 Additionally, it is believed that voiatile anesthetics may be associated with increased ventricular action potential duration as well as prolonged QT interval.14,15 The increased usage of opioids during general anesthesia is also thought to interfere with electrophysiology studies by affecting vagal tone.16

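### Do the boundary Holter at 6 weeks and the silence on missed Holters undermine the AF recurrence comparison?

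*Combined protocol and SAP*

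**What the plan says.** Three parts of the combined protocol and SAP bear on this.

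- **SF - HIPAA, item 1.** Recurrence is "defined as recurrence of paroxysmal atrial fibriliation recurring at any time after 6 weeks past the day of" the procedure. The follow-up is routine: "As standard of care these patients are followed up with Holter monitoring for a period of 6 months". Recordings cover "48 hour time periods immediately post-procedure, 2 weeks, 6 weeks, 4 months and 6 months post procedure". No visit windows are given.
- **SF - Risks, Discomforts, Potential Harms and Benefits, withdrawal criteria.** Patients with incomplete Holters stay in the study, and "the missed data fields will not be evaluated for that specific patients".
- **SF - Research Description, secondary hypothesis.** The laryngeal mask is expected to be "superior or non-inferior to endotracheal tube in duration of fluoroscopy, post procedure side effects, patient satisfaction and recurrence of PAF". No margin or analysis method is stated for recurrence.

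Two further places concern how recurrence could come to light. HIPAA item 2 says information is gathered by "reviewing data from the medical record of VCU Health" as well as by survey. The section on standard-of-care costs lists "post procedure holter monitors and post procedure office visits" among routine care.

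**The concern.** The outcome is any recurrence after a cut-off, so a patient's chance of being recorded as recurrent depends on how often the patient was monitored after it. Two things make that number uncertain.

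First, the 6-week Holter sits on the cut-off. Done slightly early, it falls outside the definition; done slightly late, it falls inside. Patients may therefore have two or three scheduled recordings that count.

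Second, the missing-data rule is written for data fields, while the outcome belongs to the patient. Someone with a negative 4-month Holter and no 6-month Holter could be called recurrence-free, missing or censored. If called recurrence-free, that patient is compared with others who had two chances of detection.

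Two harms could follow. If attendance differed by airway group, identical arms would appear to differ. If attendance were equally poor in both, recorded rates would fall and an absolute difference would shrink, which makes a non-inferiority conclusion easier to reach. The plan is also not explicit on whether AF found at an office visit counts.

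**Working it through.** **The plan's own figure.** The only sample-size figure is for procedure length: SD 0.9 h, margin 0.5 h, n = 82. With one-sided 5% and 80% power (neither is stated), n per arm = 2 × 0.9² × (1.645 + 0.842)² / 0.5² ≈ 40.1, rounded up to 41, so 82 in total. Allowing 5% dropout, 82/0.95 = 86.3, rounded up to 87. The figure reproduces, and the recurrence question does not affect it.

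**Assumed inputs.** The documents give no recurrence rate, detection rate or Holter attendance. Three models span the possibilities, with *k* the number of Holters that count:

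- A, independent recordings with 15% positive each: 1 − 0.85^k
- B, 30% of patients truly recur and each Holter detects 30% of them: 0.30 × (1 − 0.70^k)
- C, full persistence (a patient positive once is positive every time): 15% for any *k* ≥ 1

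| k | A | B | C |
|---|---|---|---|
| 1 | 15.0% | 9.0% | 15% |
| 2 | 27.75% | 15.3% | 15% |
| 3 | 38.6% | 19.7% | 15% |

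**Unequal attendance, identical arms.** Suppose a share *m* of an arm misses one of the two later Holters and is counted on the remaining one. The recorded rate is m × rate(1) + (1 − m) × rate(2). The SE of the difference uses 44 per arm.

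- 40% vs 10%, A: 0.4 × 15 + 0.6 × 27.75 = 22.65%; 0.1 × 15 + 0.9 × 27.75 = 26.48%. Difference 3.8 points, SE 9.2, ratio 0.42.
- 40% vs 10%, B: 12.78% vs 14.67%. Difference 1.9 points, SE 7.3, ratio 0.26.
- 20% vs 10%: A 25.20% vs 26.48%, 1.3 points; B 14.04% vs 14.67%, 0.6 points.
- C: 0 throughout. Equal attendance: 0 in every model.

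A harsher case lets every Holter be attended by 95% in one arm and 75% in the other, with independent recordings. With per-Holter positivity *p*, the rates are 1 − (1 − 0.95p)^k and 1 − (1 − 0.75p)^k. For p = 0.10, k = 2 this is 18.1% vs 14.4%, or 3.7 points (SE 7.9, ratio 0.47). For p = 0.20, k = 3 it is 46.9% vs 38.6%, or 8.3 points (SE 10.5, ratio 0.79).

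**Equal attendance, arms that truly differ.** Take true recurrence of 30% vs 40% and 30% detection per Holter.

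- Both later Holters attended: 0.30 × 0.51 = 15.3% vs 0.40 × 0.51 = 20.4%, 5.1 points.
- 25% of each arm miss one: 0.25 × 9 + 0.75 × 15.3 = 13.7% vs 0.25 × 12 + 0.75 × 20.4 = 18.3%, 4.6 points.

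The fall from 10 points to 5.1 comes from intermittent monitoring with full attendance. Missed Holters add about 0.5 point.

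**The 6-week Holter.** Counting it for everyone moves the rate from 15.3% to 19.7% (B) or from 27.75% to 38.6% (A), equally in identical arms. In the 30% vs 40% example the difference becomes 0.30 × 0.657 = 19.7% vs 0.40 × 0.657 = 26.3%, or 6.6 points against 5.1.

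**The visit-by-visit alternative.** Comparing only attended Holters, one visit at a time, removes the attendance artefact if missing a Holter is unrelated to rhythm within arm and visit. In the same example it gives 0.30 × 0.30 = 9.0% vs 0.40 × 0.30 = 12.0%, or 3.0 points.

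**The case for a change.** The strongest argument for a change does not depend on unequal attendance. Two analysts working from this text could report recurrence rates 4.4 points apart (B: 19.7 − 15.3) or 10.8 points apart (A: 38.6 − 27.75), depending on whether the 6-week Holter counts, and could choose after seeing the data. The direction of the missed-Holter effect is also certain: adding recordings can never lower the chance of a positive one. Under the harsher attendance case the false difference reaches 0.79 SE, which is not trivial.

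Part of this stands. The text leaves the classification open, and a written rule would be tidier. The rest carries less weight:

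- The 6-week choice shifts the level of both arms and has no evident link to airway group. Recordings are dated, so the definition can be applied by date, or the visit can be included or excluded for everyone.
- Nothing in the documents suggests that attendance at routine Holters weeks or months later depends on the airway device. The 0.79 SE figure needs a 20-point attendance gap at every visit as well as independent recordings.
- The missing-data rule does not score a missed Holter as negative. The distortion arises only if an analyst chooses to do so.
- The definition is not confined to Holter findings and the medical record is a stated source, so AF documented there after 6 weeks meets it on a plain reading.

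The absence of a recurrence margin is a separate matter and would remain however Holters were classified.

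**Conclusion.** No change to the plan follows. This is missing detail on one secondary outcome, of a kind analysts can fill sensibly by treating the 6-week recording alike for all patients, not reading a missed Holter as a negative one, and showing Holters completed by arm. The primary outcome and its sample size are untouched.

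Under the assumed models, equal attendance gives no spurious difference. A 20% vs 10% split gives 0 to 1.3 points and a 40% vs 10% split gives 0 to 3.8, at most about 0.4 SE. Only the harsher assumption of 95% vs 75% attendance at each of two or three independent Holters, with 10% to 20% positivity, gives 3.7 to 8.3 points. Equal non-attendance costs about half a point of an already attenuated difference. These sizes would need revisiting if attendance proved clearly different by arm.

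The visit-by-visit analysis would not be a clear gain. It replaces a patient-level any-time outcome with a per-Holter rate and shrinks the illustrative difference to 3.0 points, below the 4.6 left by missed Holters. It therefore worsens the attenuation that made the gap look important for non-inferiority.
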